10.4. Statistical Analyses

10.4.1. Safety Analyses

Safety data will be presented in tabular and/or graphical format and summarised descriptively according to GSK's Integrated Data Standards Library (IDSL) standards.

All safety analyses will be performed on the Safety Population.

Endpoint	Statistical Analysis Methods
Primary	All safety evaluations will be based on the Safety population. Clinical interpretation will be based on the review and displays of adverse events, clinical laboratory values, vital sign measurements and 12-lead ECG monitoring.

10.4.2. PK Analyses

Endpoint	Statistical Analysis Methods
Secondary	
PK analyses will be described in the RAP.
 
The PK of TID and BID dosing on Day 1 in Part A will be evaluated. In Part B the comparisons of interest will be:
 
The PK profile following the 1st dose of the day following administration in the fed state (standard meal on Day 9 and high fat meal on Day 11) or in the fasted state (Day 14).
 
The pharmacokinetic profile following the 1st dose on Day 14 (fasted) and the 1st dose on Day 1 (fasted);
 
Pharmacokinetic data will be listed and presented in graphical form and will be summarized descriptively.
 
Statistical summaries of the PK parameter data will be the responsibility of

Endpoint	Statistical Analysis Methods
	
Clinical Statistics, GlaxoSmithKline.
 
Descriptive statistics (n, arithmetic mean, standard deviation, 95% CI, minimum, median and maximum,) will be calculated for all pharmacokinetic parameters by treatment. In addition, for loge-transformed variables geometric mean, 95% confidence interval and %CVb ($100 * \sqrt{\exp(SD_2) - 1}$) will be provided, where the SD is the standard deviation of log-transformed data.

10.4.3. Other Analyses

Descriptive statistics (n, arithmetic mean, standard deviation, 95% CI, minimum, median and maximum) of circulating glucuronide metabolite (M8; GSK3562183) and des-methyl metabolite will be investigated in healthy subjects after single-day and repeat dosing of GSK2982772.

10.4.4. Interim Analyses

An interim analysis may be performed during the study on completed cohorts in Part A and Part B of the study to aid internal decision making only. There will be no changes to the study design or planned number of subjects in future cohorts as a result of the interim analysis.

For Parts A and B of the study, interim PK analyses will be performed on plasma GSK2982772 concentration-time data generated during the conduct of this study.

The decision to proceed to higher dose strengths will be made by the DEC based on assessment of safety, tolerability and pharmacokinetic data at the preceding dose. The exception to this will be in Part A where only a safety assessment (not PK) for the 120 mg TID dose will be performed. To date, the PK of GSK2982772 has been well-characterised up to 120 mg BID in the FTiH study and the 120 mg TID for Part A represents a 50% increase in dose where PK simulations are predictable. This analysis can include review of individual subject data, summaries, graphical presentations and/or statistical analysis.

The RAP will describe the planned interim analyses in greater detail.

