3.3.1. Risk Assessment

Potential Risk of Clinical Significance	Summary of Data/Rationale for Risk	Mitigation Strategy
Investigational Product (IP) GSK2982772		
Central Nervous System (CNS) Effects	
Non-Clinical Data:
 
In the 4-week GLP toxicology study, CNS findings were observed in 2/12 monkeys which were administered 100 or 300 mg/kg/day. CNS findings included uncoordination, irregular gait, trembling, hunched appearance and decreased activity. The NOAEL for this study was determined at 10 mg/kg/day.
 
In the 13-week GLP toxicology study, there were no CNS findings observed in monkeys administered 10, 30 or 100 mg/kg/day. The NOAEL for this study was determined at 30 mg/kg/day.
 
Clinical Data:
 
A FTiH study with single ascending and multiple ascending dose study has been performed in 67 healthy male volunteers to date (see IB [GlaxoSmithKline Document Number 2014N204126_02]). No drug-associated CNS adverse events (AEs) were identified and no Serious AEs (SAEs) were reported.
	
Subject Selection:
 
Subjects with known history of significant neurologic disorders including but not limited to progressive multiple sclerosis (MS), Amyotrophic lateral sclerosis (ALS), Alzheimer's and dementia will be excluded.
 
Individuals with potentially increased susceptibility for neurologic effects will be excluded based on medical history at screening.
 
Subject Monitoring:
 
Subjects will be monitored for standard CNS-related AEs.

Potential Risk of Clinical Significance	Summary of Data/Rationale for Risk	Mitigation Strategy

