5.7. Dose Justification

An adaptive dose-escalation approach, guided by the observed safety, tolerability and plasma PK exposure will be taken to allow an efficient evaluation of a range of doses above the 120 mg BID dose that was evaluated in the FTiH study.

The initial starting dose planned is 120 mg TID and the maximum daily dose is anticipated to be approximately 720 mg administered as 240 mg TID and 360 mg BID.

For doses of up to 120 mg BID, the pharmacokinetics of GSK2982772 are approximately linear. Please see GSK2982772 IB [GlaxoSmithKline Document Number [2014N204126_02](#)]. After attainment of C_{max} , at approximately 2 hours post-dose, GSK2982772 concentrations decline rapidly until about 12 hours post-dose, with a $t_{1/2}$ of approximately 2 to 3 hours. The majority of the systemic exposure to GSK2982772 is observed within the first 12 hours after administration. Following repeat dosing of GSK2982772, there is no evidence of drug accumulation for either a QD or BID dosing regimen. The major circulating metabolite is an N-glucuronide which accounts for approximately 70% of drug related material in plasma. Since glucuronidation is a high

capacity clearance mechanism it is unlikely that the kinetics of GSK2982772 will become saturable with more frequent dosing nor at the higher doses planned in the current study.

Due to the short half-life of GSK2982772 (~2-3 hr), it is expected that steady-state will be achieved by Day 2 of dosing and that negligible accumulation will be observed. Therefore, the PK safety margins described for Day 1 and for Day 14 of dosing will be similar.

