8. DISCONTINUATION CRITERIA

8.1. Discontinuation of Study Treatment

8.1.1. Dose Modification/Stopping Criteria

This protocol allows some alteration from the currently outlined dosing schedule, but the maximum total daily dose will not intentionally exceed the 13-week NOAEL exposure in monkeys. Currently, the highest planned dose is 720 mg/day of GSK2982772.

The decision to proceed to the next dose level of GSK2982772 in each part of this study will be made by the DEC, including the Medical Monitor and the Investigator and relevant clinical site staff (see Section 10.5) based on safety, tolerability, and preliminary PK data obtained in at least 6 subjects (through at least 24 hours post-dose) with at least 6 subjects having received active treatment (GSK2982772) at the prior dose level. The actual doses to be administered may be adjusted based on safety, tolerability and preliminary PK data at previous dose levels; these dose adjustments may involve either an increase or a decrease in the planned dose, but will not exceed the PK criteria defined in Section 8.1.2. Planned doses may also be repeated.

The Principal Investigator and the GSK Medical Monitor will review the following and dosing **will be** halted and progression to the next higher dose level stopped if:

- One (1) or more subjects experience a SAE which has a reasonable possibility of relation to study drug.
- Two (2) or more subjects experience a severe or clinically significant non-serious AE (based upon investigator judgment) which has a reasonable possibility of relation to study drug.
- Two (2) or more subjects in a Part A cohort or 3 or more subjects in a Part B cohort experience the same AE of moderate severity which has a reasonable possibility of relation to study drug.
- Consistent Common Terminology Criteria for Adverse Events (CTCAE) Nervous System AEs of any grade occur across subjects that have a reasonable possibility of relation to study drug.

If dosing is halted and if deemed acceptable by GSK internal safety review to proceed with or modify dose escalation to further characterize the safety profile, a formal request with appropriate data and substantial amendment will be submitted to MHRA (Medicines and Healthcare Products Regulatory Agency) for approval.

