10.5. Dose Escalation Committee

The decision to proceed to the next dose level of GSK2982772 in each Cohort will be made by a DEC consisting of the Principal Investigator (or appropriate designee), Medical Monitor, GSK Clinical Investigational lead and/or Study Team Leader, GSK Pharmacokineticist, a GSK GCSP representative and GSK Statistician. All GSK personnel including the GSK Statistician and the GSK Pharmacokineticist will remain unblinded throughout the course of the study.

For Part A, dose escalation decisions will be based on data obtained from 6 or more subjects receiving GSK2982772 at the prior dose level. The review of the data set will consist at a minimum of: listings of all AEs, clinical laboratory results, flagged vital signs, flagged findings during continuous cardiac monitoring (telemetry), ECG and PK results derived from 24-hour plasma profiles.

The decision and selection of dose to proceed to Part B, will be made by the DEC based on safety, tolerability, and PK data from the same dose levels evaluated in Part A.

For Part B, dose escalation decisions will be based on data obtained from 6 or more subjects receiving GSK2982772 at the prior dose level. The review of the data set will consist at a minimum of: listings of all AEs, clinical laboratory results, flagged vital signs, flagged findings during continuous cardiac monitoring (telemetry) and ECG findings through Day 16 of the previous cohorts(s) in Part B. Also included will be any PK results derived through at least Day 7 of the previous cohort(s).

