2. SUMMARY OF KEY PROTOCOL INFORMATION

2.1. Changes to the Protocol Defined Statistical Analysis Plan

Changes from the originally planned statistical analysis specified in the protocol are outlined in Table 1.

Table 1 Changes to Protocol Defined Analysis Plan

Protocol	Reporting & Analysis Plan	
Statistical Analysis Plan	Statistical Analysis Plan	Rationale for Changes
An interim analysis may be performed during the study on completed cohorts in Part A and Part B of the study to aid internal decision making only. The RAP will describe the planned interim analyses in greater detail.	No formal IA will be conducted during the study.	The DEC make decisions on proceeding to higher dose strengths based on assessment of safety, tolerability and pharmacokinetic data at the preceding dose only.
Protocol Section 10.3 references an 'Enrolled population'.	RAP uses the 'Randomised Population'.	The population was renamed to match the current IDSL guidance.

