3. PLANNED ANALYSES

3.1. Interim Analyses

No interim analyses will be performed. The decision to proceed to higher dose strengths will be made by the Dose Escalation Committee (DEC) based on assessment of safety, tolerability and pharmacokinetic data at the preceding dose.

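### Protocol 10.4.4 lets the Part A step from 120 to 240 mg TID be decided without PK, contradicting 8.1.1 and 10.5, and its 50% rationale does not cover that doubling

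*Protocol*

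**What the plan says.** Protocol 10.4.4 (Amendment 02) first gives the general rule, that escalation rests on safety, tolerability and PK at the preceding dose. It then exempts one review: in Part A, "only a safety assessment (not PK) for the 120 mg TID dose will be performed". The reason is that PK was well characterised up to 120 mg BID in the first-in-human study and that 120 mg TID "represents a 50% increase in dose where PK simulations are predictable". The original protocol and Amendment 01 have the same clause.

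Other places state the rule without the exception:

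- Protocol 8.1.1, for each part of the study, bases escalation on safety, tolerability and "preliminary PK data obtained in at least 6 subjects (through at least 24 hours post-dose"), with at least 6 participants on active drug at the prior dose.
- Protocol 10.5 sets a minimum data set for Part A that includes "ECG and PK results derived from 24-hour plasma profiles".
- Protocol 5.7 describes escalation as "guided by the observed safety, tolerability and plasma PK exposure". This is a general approach, not an operating rule.
- SAP 3.1 and 2.3 base the decision on "assessment of safety, tolerability and pharmacokinetic data at the preceding dose". SAP 2.1, which lists departures from the protocol's analysis plan, refers to "pharmacokinetic data at the preceding dose only" and does not mention the exception.

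**The concern.** The committee cannot obey both 10.4.4 and 10.5 when it decides whether to leave 120 mg TID. Under one, measured exposure is not needed; under the other, it is part of the minimum. A reader of the study report could not tell whether the escalation complied with the protocol.

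The choice matters because the next dose in Part A is 240 mg TID, where predicted exposure comes close to the animal no-effect level. If 10.4.4 is followed, that dose rests on a prediction from first-in-human data alone, although 24-hour profiles at 120 mg TID have already been drawn in this study. The rationale offered for waiving PK concerns the move into 120 mg TID. It does not discuss the move out of it.

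**Working it through.** **1. The plan's 50%.** 120 mg BID is 2 × 120 = 240 mg/day and 120 mg TID is 3 × 120 = 360 mg/day. 360/240 − 1 = 50%, so the figure reproduces. The unit dose stays at 120 mg.

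**2. The step that the exception releases.** The Cohort 1 sequences in 7.2 put 240 mg TID directly after 120 mg TID.

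- Daily dose: 3 × 240 = 720 mg/day; 720/360 = 2.0, an increase of 100%.
- Unit dose: 240/120 = 2.0.
- Against the first-in-human maximum daily dose (120 mg BID, protocol 3.1): 720/240 = 3.0.
- Protocol 5.7 documents approximate linearity only up to 120 mg BID.

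**3. Predicted exposure.** Protocol 5.7 predicts a mean AUC(0-24) of 40.2 µg·h/mL at 240 mg TID, against a mean of 48.4 at the NOAEL: 40.2/48.4 = 83%. Scaled linearly, 120 mg TID gives 40.2 × 360/720 = 20.1, which is 42% of 48.4.

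As an illustration of spread, take the first-in-human CVb of 27.1% from 10.1, assume that it applies to AUC(0-24), and assume lognormality:

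- σ = √ln(1 + 0.271²) = 0.266.
- 95th percentile at 240 mg TID: 40.2 × exp(1.645 × 0.266) = 62.3 if 40.2 is a geometric mean. If it is an arithmetic mean, the geometric mean is 40.2/√(1 + 0.271²) = 38.8 and the percentile is 60.1.
- Share above the NOAEL mean of 48.4: 1 − Φ[ln(48.4/40.2)/0.266] = 24%, or 20% with 38.8. At 120 mg TID the same calculation gives under 0.1%.

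The limit in 8.1.2 is the highest AUC seen at the NOAEL, not the mean. That value is only in a figure not available here, so the distance to the limit cannot be computed. Cmax has more room: the 95th percentile on the same basis (mean 3.21, CVb 36.1%) is 5.4 to 5.7 µg/mL, against a limit of 12.3.

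**4. What a 120 mg TID review would give.** The 90% precision for the geometric mean AUC is exp(t × σ/√n) − 1. With 6 active participants it is exp(2.015 × 0.266/√6) − 1 = 24.5%. With 9 it is exp(1.860 × 0.266/√9) − 1 = 17.9%, the value in 10.1. That can show a material misprediction, though not a small one.

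**5. Whether the sections can be reconciled.** Reading 10.4.4 as a specific carve-out from a general rule might work against 8.1.1. It does not work against 10.5, whose paragraph is specific to Part A and is framed as a minimum. Section 8.1.2 is not contradicted, because its dose adjustment is permissive and its limit is on predicted values.

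**The case against.** The best defence is that the waiver is narrower than it looks. At 120 mg TID the unit dose is one already studied, given once more per day. Protocol 5.7 reports a half-life of 2 to 3 hours, no accumulation, and linear PK up to 120 mg BID, so exposure at 120 mg TID may fairly be called predictable. Measuring it would test the new dosing frequency but not linearity above a 120 mg unit dose. The step was a single dosing day with a sentinel pair, telemetry and an inpatient stay. Protocol 5.7 is only a general statement, and the SAP was written after Part A escalation, so it did not govern the decision. The step is in any case past.

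Most of this stands. It limits the operational conflict to 10.4.4 against 8.1.1 and 10.5, and it makes the rationale incomplete rather than irrelevant. It does not remove the conflict, and it supplies no argument for doubling the dose.

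Two stronger readings are tempting and not supported:

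- A reader might infer that a 120 mg TID review would have given the first PK in women, since the first-in-human study "has been performed in 67 healthy male volunteers to date" and this study admits women. The Amendment 01 rationale mentions a woman in Cohort 1, treatment period 2, but gives neither her treatment sequence nor any PK. Nothing shows that an active woman would have been in the review.
- A reader might infer that everyone given 240 mg TID already had a profile at half the dose. Participants in sequence PBC receive placebo first. With equal allocation (assumed), they are 3 of the 9 given 240 mg TID.

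**Conclusion.** The contradiction is real, stands in the current text, and concerns a dose escalation decision. The rationale covers a 1.5-fold rise in daily dose; the step released is 2-fold, beyond the range of documented linearity, to a predicted mean AUC(0-24) at 83% of the NOAEL mean. These ratios rest only on figures in the protocol. The percentile illustration also rests on lognormality and the first-in-human CVb.

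The finding does not extend to harm or non-compliance:

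- A reader might infer that the 8.1.2 limit was at risk or exceeded at this step. The NOAEL maximum is not available, so that cannot be shown.
- The Amendment 01 rationale reports one Cohort 1 participant with about 2-fold higher Cmax at both TID doses. That is relative to the other participants, not to the prediction, and no observed value is given.
- The footnote in SAP 5.1 records that PK stopping criteria were reached at the end of Cohort 4. It names no limit and does not link this to the Part A exception.
- The documents do not say that PK was skipped. They show only that both TID doses had been given by Amendment 01.

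The sponsor should correct this. What remains is consistency of the protocol and transparent reporting of a decision already taken.

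**What to change.** Delete the Part A exception from protocol 10.4.4. The rule is then the one already in 8.1.1 and 10.5: 24-hour PK from at least 6 active participants at 120 mg TID is reviewed before 240 mg TID is given. Because that step had been taken by Amendment 01, state in the study report which rule the committee applied and whether it had seen 120 mg TID PK first. No change of dose is proposed.

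No extra samples are needed, because the Part A schedule in 2.1 already includes TID profiles to 24 hours. The cost is assay turnaround, which the documents do not give. At the 7-day minimum washout the room is small. If the sentinel pair is dosed on Day 1 and the rest on Day 3, the last 24-hour sample falls on Day 4 and the next sentinel dose on Day 8, leaving about 4 days (this assumes that the same pair goes first again). The planned calendar is looser: 13 weeks (91 days) less 28 for screening and 14 for follow-up leaves 49 days for two intervals, or 24.5 days each. That is about 17 days per step beyond the minimum washout.

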10.5. Dose Escalation Committee

The decision to proceed to the next dose level of GSK2982772 in each Cohort will be made by a DEC consisting of the Principal Investigator (or appropriate designee), Medical Monitor, GSK Clinical Investigational lead and/or Study Team Leader, GSK Pharmacokineticist, a GSK GCSP representative and GSK Statistician. All GSK personnel including the GSK Statistician and the GSK Pharmacokineticist will remain unblinded throughout the course of the study.

For Part A, dose escalation decisions will be based on data obtained from 6 or more subjects receiving GSK2982772 at the prior dose level. The review of the data set will consist at a minimum of: listings of all AEs, clinical laboratory results, flagged vital signs, flagged findings during continuous cardiac monitoring (telemetry), ECG and PK results derived from 24-hour plasma profiles.

The decision and selection of dose to proceed to Part B, will be made by the DEC based on safety, tolerability, and PK data from the same dose levels evaluated in Part A.

For Part B, dose escalation decisions will be based on data obtained from 6 or more subjects receiving GSK2982772 at the prior dose level. The review of the data set will consist at a minimum of: listings of all AEs, clinical laboratory results, flagged vital signs, flagged findings during continuous cardiac monitoring (telemetry) and ECG findings through Day 16 of the previous cohorts(s) in Part B. Also included will be any PK results derived through at least Day 7 of the previous cohort(s).

12. APPENDICES

12.1. Appendix 1: Abbreviations and Trademarks

Abbreviations

AE	Adverse Event
ALS	Amyotrophic lateral sclerosis
ALT	Alanine aminotransferase
ANA	Anti-nuclear Antibody
API	Active Pharmaceutical Ingredient
AST	Aspartate aminotransferase
AUC	Area under the concentration-time curve
AUC ₍₀₋₇₎	Area under the concentration-time curve from time zero to 7 hours post first dose (TID dosing)
AUC ₍₇₋₁₄₎	Area under the concentration-time curve from 7 to 14 hours post first dose (TID dosing)
AUC ₍₁₄₋₂₄₎	Area under the concentration-time curve from 14 to 24 hours post first dose (TID dosing)
AUC ₍₀₋₁₂₎	Area under the concentration-time curve from 0 to 12 hours post first dose (BID dosing)
AUC ₍₁₂₋₂₄₎	Area under the concentration-time curve from 12 to 24 hours post first dose (BID dosing)
AUC ₍₀₋₂₄₎	Area under the concentration-time curve from time zero to 24 hours post first dose
AUC _(0-t)	Area under the concentration-time curve from time zero (pre-dose) to last time of quantifiable concentration within a subject across all treatments
AUC _(0-τ)	AUC from 0 hours to the time of next dosing.
BID	Twice a day
BMI	Body Mass Index
BP	Blood Pressure
CFR	Code of Federal Regulations
CI	Confidence Interval
CIOMS	Council for International Organizations of Medical Sciences
CKD-EPI	Chronic Kidney Disease Epidemiology Collaboration
C _{max}	Maximum observed concentration
CNS	Central Nervous System
CONSORT	Consolidated Standards of Reporting Trials
CPK	Creatine phosphokinase
CRF	Case Report Form
CRP	C-Reactive Protein
CSR	Clinical Study Report
C-SSRS	Columbia Suicide Severity Rating Scale
CTCAE	Common Terminology Criteria for Adverse Events
CVb	Coefficient of Variation
CYP3A4	Cytochrome P450 3A4

DEC	Dose Escalation Committee
ECG	Electrocardiogram
eGFR	Estimated glomerular filtration rate
FSH	Follicle stimulating hormone
FTiH	First Time in Human
GCP	Good Clinical Practice
GCSP	Global Clinical Safety and Pharmacovigilance
GSK	GlaxoSmithKline
HBsAg	Hepatitis B surface antigen
hCG	Human chorionic gonadotropin
HIPAA	Health Insurance Portability and Accountability Act
HIV	Human Immunodeficiency Virus
HPLC	High performance liquid chromatography
HPMC	Hydroxypropylmethyl cellulose
HR	Heart Rate
HRT	Hormonal replacement therapy
IB	Investigator's Brochure
ICF	Informed Consent Form
ICH	International Conference on Harmonisation
IDSL	Integrated Data Standards Library
IgG	Immunoglobulin G
IP	Investigational Product
IRB/IEC	The Institutional Review Board/ Independent Ethics Committee
IUD	Intrauterine device
IUS	Intrauterine hormone-releasing system
kg	Kilogram
LDH	Lactate dehydrogenase
MCH	Mean corpuscular haemoglobin
MCV	Mean corpuscular volume
mg	Milligram
mL	Millilitre
MR	Modified Release
MS	Multiple Sclerosis
MSDS	Material Safety Data Sheet
NFκB	Nuclear factor kappa-light-chain-enhancer of activated B cells
NOAEL	No observable adverse effect limit
NTI	Narrow Therapeutic Index
Pgp	P-glycoprotein
PGx	Pharmacogenetics
PK	Pharmacokinetics
PoC	Proof of Concept
PsO	Psoriasis
PSRAE	Possible Suicidality Related Adverse Event
QTc	Electrocardiogram QT interval corrected for heart rate
QTcB	Electrocardiogram QT interval corrected for heart rate using Bazett's formula

QTcF	Electrocardiogram QT interval corrected for heart rate using Fridericia's formula
RA	Rheumatoid Arthritis
RAP	Reporting and Analysis Plan
RBC	Red Blood Cell
RIP1	Receptor-interacting protein-1
SAE	Serious Adverse Event
SGOT	Serum Glutamic-Oxaloacetic Transaminase
SGPT	Serum Glutamic-Pyruvic Transaminase
SIB	Suicidal Ideation Behaviour
SoA	Schedule of Activities
SOP	Standard Operating Procedure
SRM	Study Reference Manual
SRT	Safety Review Team
SUSAR	Suspected unexpected serious adverse events
TB	Tuberculosis
TID	Three times a day
T _{max}	Time taken to maximum observed plasma drug concentration
TNF	Tumour Necrosis Factor
TNFR1	Tumour Necrosis Factor Receptor-1
UC	Ulcerative Colitis
UDP	Uridine diphosphate
µg	Microgram
UGT	Uridine 5'-diphospho-glucuronosyltransferase
UK	United Kingdom
ULN	Upper Limit of Normal
WOCBP	Woman of Child Bearing Potential

Trademark Information

Trademarks of the GlaxoSmithKline group of companies
NONE

Trademarks not owned by the GlaxoSmithKline group of companies
Quantiferon

